1.2. Schema

1.3. Schedule of Activities (SoA)

Both treatment arms will use the same Screening Table ([Table 1](#)). Separate tables have been produced for the GSK3228836 treatment period ([Table 2](#) and [Table 3](#)). Both treatment arms will use the same PegIFN Treatment Table ([Table 4](#)), Reassessment of PegIFN Eligibility Tables ([Table 5](#) and [Table 6](#); only required if participant is ineligible to start PegIFN as per [Table 4](#)) and Off Treatment Follow-up Table ([Table 7](#)).

[China specific Schedule of Activities can be found in [Appendix 7: Country-specific requirements](#)]

Instructions that are applicable to all treatment arms include:

- In selected countries/sites, participants will have the option to use a centralised home nursing provider. Only selected visits will have the option to be performed as a home visit, these will include drug administration, blood draws, participant assessments and data collection. The full specifications of the home nursing services will be outlined in the Study Reference Manual (SRM).
- Haematology (platelet count) will be analysed at a local laboratory prior to each GSK3228836 dose. The blood draw can be taken the day before GSK3228836 dosing. Results must be available prior to dosing. Haematology samples will be collected for central laboratory assessments in parallel. After GSK3228836 treatment is completed, haematology is only collected centrally on weeks of clinic visits.
- If a participant is not eligible to start PegIFN, eligibility will be reassessed. If the participant does not become eligible after 13 weeks, PegIFN will not be initiated in order to ensure participants receive at least 12 weeks of PegIFN treatment. Irrespective of the week that a participant starts PegIFN, the final dose will be given on Study Week 48 for Arm 1 and Week 36 for Arm 2 ([Figure 1](#)).
- PegIFN dosing maybe self-administered at home, where local regulations allow at the visits indicated in the SoA ([Table 4](#)).

Figure 1 Schematic of Planned GSK3228836 and PegIFN Dosing Periods and Off Treatment Follow-up Period

[figure not shown]

Table 1 Screening (All Treatment Arms)

ASSESSMENTS	
Informed Consent (obtained any time prior to screening)	X
Inclusion and exclusion criteria	X
Demography	X
Medical history (includes substance usage) and current medical conditions	X
Medication history and concomitant medication review	X
Full physical exam including height and weight	X
Vital signs	X

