4. STUDY DESIGN

4.1. Overall Design

This is a Phase IIb, multi-centre, randomised, open-label study to assess the efficacy and safety of sequential treatment with GSK3228836 (300 mg/week for 12 or 24 weeks) followed by PegIFN (180 mcg/week for up to 24 weeks) in participants with CHB on stable NA therapy. During the GSK3228836 treatment period, a 300 mg loading dose will be administered on Day 4 and Day 11. Participants will continue their NA therapy for the duration of the study.

Participants will be randomised (1:1) into one of two parallel treatment arms.

1. 300 mg GSK3228836 once/week for 24 weeks (plus loading dose on Day 4 and 11) followed by PegIFN (180 mcg/week for up to 24 weeks). Participants will be followed up for an additional 24 weeks (off-treatment phase) once PegIFN treatment is complete.

2. 300 mg GSK3228836 once/week for 12 weeks (plus loading dose on Day 4 and 11) followed by PegIFN (180 mcg/week for up to 24 weeks). Participants will be followed up for an additional 36 weeks (off-treatment phase) once PegIFN treatment is complete.

The planned duration of GSK3228836 is 24 weeks and 12 weeks in Treatment Arm 1 and 2 respectively. If a participant prematurely discontinues GSK3228836 treatment the participant is encouraged to complete the SoA as per the planned GSK3228836 dosing period. At the end of the planned GSK3228836 dosing period, participants will be re-assessed for eligibility to start PegIFN treatment based on the label.

1. Participants immediately eligible for PegIFN will begin treatment
2. Participants who are not considered eligible will be re-assessed for eligibility and may delay start of PegIFN treatment for up to 12 weeks.
3. Participants who fail to meet PegIFN eligibility criteria by PegIFN Eligibility Week 13 (i.e. can no longer receive at least 12 weeks of PegIFN treatment) will not receive treatment with PegIFN.

Note: all participants are expected to end PegIFN treatment at the same time, regardless of when they start therapy (Treatment Group 1: all participants should complete treatment by Week 48; Treatment Group 2: Week 36).

As such, the planned treatment duration with PegIFN for participants on study 209348 may vary from a minimum of 12 weeks to a maximum of 24 weeks.

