4.2.4. Supplementary Estimands

The following supplementary estimands are defined to support the primary objective.

4.2.4.1. Measuring SVR from Actual End of Treatment instead of Planned End of Treatment

The first supplementary estimand is defined in the same way as the primary estimand, except the assessment time frame for participants achieving SVR will be 24 weeks after the actual end of treatment. The estimand strategy for handling treatment discontinuation unrelated to wide disruptive events will be while-on-treatment, which calculates the actual duration from the first to the last dose of treatment received. See Section 4.2.1 for additional details.

4.2.4.2. Measuring SVR from Actual End of Treatment by Categorical Subgroups of PegIFN Treatment Duration

The second supplementary estimand supporting the primary objective measures SVR from actual end of treatment by categorical subgroups of PegIFN treatment duration.

The second supplementary estimand is defined as:

- **Population:** Participants with CHB on stable NA therapy that are eligible for PegIFN.
- **Treatment:** 300 mg GSK3228836 for 12 or 24 weeks followed by up to 24 weeks of PegIFN therapy while on stable NA therapy.
- **Variable:** The percentage of participants that achieve SVR for 24 weeks after the actual end of sequential treatment without the use of rescue medication

- **Intercurrent Events:**
 - Significant interruption in or non-adherence to PegIFN related or unrelated to WDEs will be analysed as collected (treatment policy strategy).
 - Discontinuation and delayed start of PegIFN related or unrelated to WDEs will be handled by calculating the actual duration using the first to the last dose of PegIFN received (while-on-treatment strategy).
 - Use of rescue medication will be incorporated in the definition of the endpoint (composite strategy).
- **Population Summary:** The percentage of participants achieving SVR for 24 weeks after the actual end of treatment by PegIFN treatment duration categorical grouping of at least 12, 16, 20, and 24 weeks of PegIFN treatment in each treatment arm.

4.2.4.3. Measuring SVR from Planned End of Treatment for Participants who Received At Least Twelve Doses of PegIFN

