The third supplementary estimand examines the effect of the intercurrent event of a participant failing to meet PegIFN eligibility criteria by PegIFN Eligibility Week 13 (i.e. can no longer receive at least 12 weeks of PegIFN treatment). The estimand strategy for this intercurrent event will be principal stratum, which restricts the population to participants for whom the intercurrent event did not occur. The third supplementary estimand is defined as:

- **Population:** Participants with CHB on stable NA therapy that have received at least 12 doses of PegIFN
- **Treatment:** 300 mg GSK3228836 for 12 or 24 weeks followed by up to 24 weeks of PegIFN therapy while on stable NA therapy.
- **Variable:** The percentage of participants that achieve SVR for 24 weeks after the planned end of sequential treatment without the use of rescue medication
- **Intercurrent Events:**
 - For discontinuation of, interruption in, or non-adherence to GSK3228836 or PegIFN unrelated to any wide disruptive events (such as COVID-19 pandemic), the data will be analysed as collected (treatment policy strategy).
 - For participants that are ineligible to receive PegIFN, the data will be analysed as collected (treatment policy strategy).
 - Use of rescue medication will be incorporated in the definition of the endpoint (composite strategy).
 - For wide disruptive events (such as COVID-19 pandemic) leading to discontinuation of, significant interruption in, or non-adherence to GSK3228836 and PegIFN, data collected after the intercurrent event will be set to missing and the response will be imputed assuming missing at random in the Bayesian model (hypothetical strategy).

- **Population Summary:** The percentage of participants in each treatment group who achieve SVR for 24 weeks after the planned end of sequential treatment without use of any rescue medication.

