4.5.1. Extent of Exposure

Extent of exposure will be summarized by presenting number of participants in various exposure duration categories, overall duration of exposure, and study intervention compliance.

Number of days of exposure to study drug will be calculated separately for GSK3228836 and PegIFN based on the formula:

- $\text{Duration of Exposure in Days} = \text{Last injection date} - \text{First injection date} + 1$

The duration of exposure in weeks will be calculated as duration of exposure in days divided by 7.

The cumulative actual dose will be calculated separately for GSK3228836 and PegIFN based on the formula:

- $\text{Cumulative Actual Dose} = \text{Sum of Dose administered during GSK3228836 or PegIFN dosing period}$

The dose intensity (mg/wk) will be calculated separately for GSK3228836 and PegIFN based on the formula:

- $\text{Dose Intensity} = \text{Cumulative Actual Dose} / \text{Total Actual Number of Weeks of Dose administration}$

The cumulative injected volume will be calculated separately for GSK3228836 and PegIFN based on the formula:

- $\text{Cumulative Injected Volume} = \text{Sum of Injected Volume during GSK3228836 or PegIFN dosing period}$

The weekly injected volume (mL/wk) will be calculated separately for GSK3228836 and PegIFN based on the formula:

- $\text{Weekly Injected Volume} = \text{Cumulative Injected Volume} / \text{Total Actual Number of Weeks of Dose administration}$

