6.1.5. Study Intervention Compliance

A summary of overall compliance for GSK3228836 and PegIFN based on the exposure data will be produced. Overall compliance will be summarized using descriptive statistics as well as the categories <80%, 80%-100%, and >100%.

Compliance will be summarized both in terms of number of injections administered and total dose received during the planned on-treatment period.

Percentage of compliance will be calculated as follows:

$$\text{Study intervention Compliance (\%)} = (\text{Number of actual doses}^{[1]} / \text{Number of planned doses}) * 100$$

$$\text{Study dose Compliance (\%)} = (\text{Total Cumulative Actual Dose}^{[2]} / \text{Total Cumulative Planned Dose}) * 100$$

- 1) GSK3228836 :- The planned number of doses are 26 or 14 for Arm 1 & Arm 2 respectively. The Planned Total Cumulative Dose is calculated by multiplying number of planned doses and dose that is, 300 mg.

$$\text{Planned Total Cumulative Dose} = \text{Number of planned doses} * 300 \text{ mg}$$

- 2) PegIFN: - The planned number of doses are 24 if subject becomes eligible for PegIFN Week 1. If subject becomes eligible after PegIFN Week 1, then follow Protocol table 6 to identify number of planned doses –

Table 6 PegIFN Dosing for Participants becoming Eligible for PegIFN after Week 1

Become Eligible for PegIFN at PegIFN Eligibility Week (Table 5)	PegIFN Dosing (Table 4) should continue until PegIFN Dosing Week
2	23
3	22
4	21
6	19
8	17
10	15
13	12

The Planned Total Cumulative Dose is calculated by multiplying number of planned doses and dose that is, 180 mcg.

$$\text{Planned Total Cumulative Dose} = \text{Number of planned doses} * 180 \text{ mcg}$$

[1] : Subject might receive reduced dose that is smaller than the number of injections. Reduced dose should be still counted as ‘one’ dose for *Number of actual doses* calculations.

[2] : Refer to SAP Section 4.5.1

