	302	289	316	Off-Treatment Week 8
	330	317	351	Off-Treatment Week 12
	372	352	393	Off-Treatment Week 18

Analysis Set / Domain	Target study day	Analysis Window		Analysis Timepoint
		Start day	End day	
	414	394	435	Off-Treatment Week 24
	456	436	477	Off-Treatment Week 30
	498	478	518	Off-Treatment Week 36

* Only if subject started PegIFN treatment.

1. Week x includes on-treatment weeks 5 – 24 for treatment with GSK3228836.
2. Week y includes on-treatment weeks 1 – 24 for treatment with PegIFN.
3. Week u includes PegIFN Eligibility weeks 1 – 13.
4. Week v includes PegIFN Eligibility weeks 14 – 24.
5. z is the total number of PegIFN ineligibility weeks prior to PegIFN treatment.
6. Visit windows are to be used for windowing of Early Termination visits only.

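### Counting PegIFN duration from first to last dose gives a full 24-dose course 23.14 weeks and a 12-dose course 11.14, so each misses its own cut-point in the second supplementary estimand

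*SAP*

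**What the plan says.** SAP 4.2.4.2 relates SVR, measured from actual end of treatment, to the length of PegIFN treatment. Discontinuation and delayed start are "handled by calculating the actual duration using the first to the last dose of PegIFN received (while-on-treatment strategy"), and results are summarised "by PegIFN treatment duration categorical grouping of at least 12, 16, 20, and 24 weeks of PegIFN treatment in each treatment arm". Protocol 9.4.2.2 has the same first-to-last-dose rule and leaves the groupings to the analysis plan. SAP 4.2.4.2 gives no counting convention, rounding rule or tolerance.

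The only formula in the SAP that expresses a treatment duration in weeks is in 4.5.1: last injection date minus first injection date, plus 1, and then "The duration of exposure in weeks will be calculated as duration of exposure in days divided by 7".

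Elsewhere a weekly dose counts as a week of treatment:

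- SAP 6.1.5: "The planned number of doses are 24 if subject becomes eligible for PegIFN Week 1". Protocol Table 6 reduces this to 12 doses for a participant who becomes eligible at Eligibility Week 13.
- Protocol 1.3: after Week 13 without eligibility, "PegIFN will not be initiated in order to ensure participants receive at least 12 weeks of PegIFN treatment".
- Protocol 4.1: planned PegIFN duration "may vary from a minimum of 12 weeks to a maximum of 24 weeks".
- SAP 4.2.4.3 (third supplementary estimand), population: "Participants with CHB on stable NA therapy that have received at least 12 doses of PegIFN".

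**The concern.** With weekly injections, n doses contain n − 1 intervals. A first-to-last-dose span therefore drops the week that follows the last injection, and a course of exactly 12, 16, 20 or 24 doses lands just under the cut-point of the same number. Two of those numbers are the planned extremes of this trial: 24 doses is the full course and 12 is the shortest course the protocol permits.

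The estimand exists to show how SVR varies with the amount of PegIFN received when participants start late or stop early. If the rule is followed literally, the full-course row has almost nobody in it, and a reader could conclude that hardly anyone completed PegIFN. Participants who took every dose open to them after a Week 13 start would drop out of the table, while the third supplementary estimand counts the same people in.

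**Working it through.** **Inputs**

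- Target day of PegIFN Dosing Week y (SAP Table 19): Arm 1, 1 + 7 × (23 + y + z); Arm 2, 1 + 7 × (11 + y + z). Per the footnote, "z is the total number of PegIFN ineligibility weeks prior to PegIFN treatment".
- Doses by eligibility week: protocol Table 6, repeated in SAP 6.1.5.
- Duration in weeks: (last − first + 1)/7 from SAP 4.5.1, and (last − first)/7 as the plain reading of 4.2.4.2.
- Visit window in the PegIFN period: ±3 days (protocol Table 4).

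**Reproducing the plan's own figure.** With y = 24 and z = 0, Arm 1 gives 1 + 7 × 47 = 330 and Arm 2 gives 1 + 7 × 35 = 246. These are the end-of-PegIFN target days in SAP Tables 2 and 3.

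**Full course (z = 0, 24 doses).** First dose: Arm 1, 1 + 7 × 24 = Day 169; Arm 2, 1 + 7 × 12 = Day 85.

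- 330 − 169 + 1 = 246 − 85 + 1 = 162 days; 162/7 = 23.14 weeks.
- Without the +1: 161/7 = 23.0 weeks.

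**Week 13 start (z = 12, 12 doses).** First dose: Arm 1, Day 253; Arm 2, Day 169. Last dose: Day 330 and Day 246.

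- 330 − 253 + 1 = 246 − 169 + 1 = 78 days; 78/7 = 11.14 weeks.
- Without the +1: 77/7 = 11.0 weeks.

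**All planned schedules on target days (identical in both arms)**

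| Eligible at week | Doses | Days (with +1) | Weeks | Highest group reached | Highest group by dosing weeks |
|---|---|---|---|---|---|
| 1 | 24 | 162 | 23.14 | ≥20 | ≥24 |
| 2 | 23 | 155 | 22.14 | ≥20 | ≥20 |
| 3 | 22 | 148 | 21.14 | ≥20 | ≥20 |
| 4 | 21 | 141 | 20.14 | ≥20 | ≥20 |
| 6 | 19 | 127 | 18.14 | ≥16 | ≥16 |
| 8 | 17 | 113 | 16.14 | ≥16 | ≥16 |
| 10 | 15 | 99 | 14.14 | ≥12 | ≥12 |
| 13 | 12 | 78 | 11.14 | none | ≥12 |

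Reaching 12, 16, 20 or 24 weeks takes 13, 17, 21 or 25 weekly doses. A participant who stops early after exactly 16 or 20 weekly doses is therefore also placed one group too low.

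**Visit-window shifts.** Let the first dose move by a days and the last by b days, each from −3 to +3, giving 7 × 7 = 49 pairs.

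- 24 doses: 162 − a + b ≥ 168 requires b − a = 6, which is 1 pair (first dose 3 days early, last dose 3 days late). The range is 22.29 to 24.00 weeks.
- 12 doses: 78 − a + b ≥ 84 is the same single pair. The range is 10.29 to 12.00 weeks.
- Without the +1: no pair reaches either cut-point.
- 21 and 17 doses: 141 − a + b < 140 and 113 − a + b < 112 each hold in 15 of 49 pairs, so these correctly placed courses can also slip.
- Adding 7 days instead of 1: 168 − a + b ≥ 168 and 84 − a + b ≥ 84 each hold in 28 of 49 pairs (57%). This puts the two courses exactly on the cut-point but does not secure them there.

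**The case against.** The strongest reply is that 4.2.4.2 does not cite the 4.5.1 formula, which belongs to the safety exposure summary. On that view the SAP has left a counting rule unstated and no printed figure is wrong. The SAP also credits the last dose with its week in one place: Table 14 runs the PegIFN Treatment Period for events up to 7 days after the last dose. On target days that is Day 169 up to Day 337, or 168 days = 24 weeks; for a Week 13 start it is Day 253 up to Day 337, or 84 days = 12 weeks. A programmer could adopt that convention, or the Output and Programming Specifications could hold a rounding rule. The groups are also cumulative, so full completers still appear under ≥12, ≥16 and ≥20. Finally, the second and third supplementary estimands measure different things (elapsed time and doses), so some difference in membership is to be expected.

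Part of this stands. Applying 4.5.1 is an inference, the programming specifications are not among the documents, and the loss is one row of a descriptive table plus the Week 13 starters, whose number is unknown. The main point survives because plain last minus first, which is what 4.2.4.2 literally says, gives 23.0 and 11.0 and fails as well. Rounding to the nearest week gives 23 and 11. Table 14 is a safety-period rule that 4.2.4.2 does not invoke; it shows that the estimand's rule departs from how the plan counts weeks elsewhere. The estimands may differ in definition, but the protocol sets the Week 13 limit so that these participants get at least 12 weeks, and a 12-week group that excludes them contradicts that purpose.

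**Conclusion.** The rule and the cut-points in 4.2.4.2 do not fit together, and the rule is wrong as written. On schedule, the full course scores 23.14 weeks (23.0 without the +1) and the shortest planned course 11.14 (11.0), in both arms. The ≥24-week group is empty on target days and stays nearly so if doses keep to the ±3-day window. Fully adherent Week 13 starters belong to no group.

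This assumes weekly dosing on the Table 19 target days and no unstated rounding or week-counting rule. The 1-in-49 figure counts possible shifts; reading it as a proportion of participants would require the shifts to be independent and uniform. Doses given outside the window could move individuals either way, and the documents hold no actual dosing dates.

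The consequence is limited to this one descriptive supplementary estimand. The primary analysis, the arm comparison and the exposure summaries are unaffected. It should be corrected, but it does not threaten the trial's main conclusions.

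**What to change.** In SAP 4.2.4.2, define PegIFN duration in dosing weeks: the scheduled PegIFN Dosing Week number (protocol Tables 4 and 6) of the last dose received, with the first dose as week 1. A course of 24 weekly doses is then 24 weeks and one of 12 is 12 weeks, whatever the visit-window shifts. Doses missed between the first and the last remain ignored, as the treatment policy strategy requires. For a dose recorded away from a scheduled visit, the same sentence can assign the week from the Table 19 PegIFN target days; at 7-day spacing, ±3 days covers every calendar day.

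This is preferable to replacing +1 with +7, which leaves the 24- and 12-dose courses at the mercy of a one-day shift.

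It would also help, though it is optional, to show counts in exclusive bands (<12, 12–15, 16–19, 20–23 and 24 dosing weeks) beside the cumulative groups. SAP 4.5.1 can stay as it is.

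The cost is one line of SAP text and re-programming of one derived variable. No data collection, dosing or design element changes.

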4.2.5. Additional Estimands

The following additional estimands are included to support the primary objective.

4.2.5.1. Using a Modified Definition of SVR

Note for this section: upon review of AIA results, this definition does not meet the scientific intent of the modified definition of SVR. The definition of modified SVR described in this section will be programmed as is. The intended application of this definition will be documented in note to file (NTFs) for this study and for B-clear (209668).

An additional estimand is defined in the same way as the primary estimand, except the population summary is defined using a modified definition of sustained virologic response (SVR) for 24 weeks after the planned end of sequential treatment (EoT) in the absence of rescue medication. The modified definition of SVR is observing HBsAg <LLOQ and HBV DNA <LLOQ at each analysis window in the 24 weeks after the planned end of sequential treatment (EoT). Any observation of HBsAg \geq LLOQ or HBV DNA \geq LLOQ at a visit must be confirmed individually at a consecutive visit (including unscheduled visits or the first visit after the end of the analysis window). If the consecutive visit for the same parameter is also \geq LLOQ, the SVR status for the participant at the initial visit will be an SVR non-responder. If the consecutive visit for the same parameter is also <LLOQ, the SVR status for the participant at the initial visit will be an SVR responder under the modified definition.

4.2.5.2. Impact of WDE on SVR

An additional estimand is defined in the same way as the primary estimand, except for how the subjects with missing visits due to a WDE leading to discontinuation of, interruption in, or non-adherence to GSK3228836 or PegIFN are handled. For these participants that restart GSK3228836 or PegIFN, data will be analysed as collected (treatment policy strategy).

4.3. Secondary Endpoint Analyses

4.3.1. Secondary Endpoints

For the secondary end-points relating to “Achieving HBsAg <LLOQ and HBV DNA <LLOQ”, in Section 4.3.1, the same analysis visit windows for Arm 1 and Arm 2 will be used as defined in Table 2 Table 1 and Table 3 respectively.

For other secondary endpoints (actual values and change from baseline over time, antibody levels over time, etc.) the data will be summarized as collected. Three groups of estimands are defined below for the key secondary efficacy objectives.

4.3.1.1. Efficacy of GSK3228836 and PegIFN Sequential Therapy on Biomarkers and Virus Specific Antibody Responses

The estimand strategy supporting this secondary objective is defined below. Missing data for variables defined below, except for time to ALT normalisation, will be analysed as collected. Only available data will be summarised.

- **Population:** Participants with CHB on stable NA therapy; For the time to ALT normalisation variable, population will be aforementioned participants with baseline ALT >ULN.
- **Treatment:** 300 mg GSK3228836 for 12 or 24 weeks followed by up to 24 weeks of PegIFN therapy while on stable NA therapy.
- **Intercurrent Events:**
 - Discontinuation of, interruption in, and non-adherence to GSK3228836 and PegIFN analysed as collected (treatment policy).
 - PegIFN ineligibility will be analysed as collected (treatment policy)
 - Rescue medication will be analysed as collected (treatment policy), except for ALT normalisation which can only be achieved in the absence of rescue medication.
 - Wide disruptive events (such as COVID-19 pandemic) leading to discontinuation of, interruption in, or non-adherence to GSK3228836 and PegIFN will be analysed as collected (treatment policy strategy).

Categorical Variables

The following categorical variables are defined for the objective:

- Achieving HBsAg <LLOQ and HBV DNA <LLOQ at two time points: (1) the planned end of treatment analysis window and (2) at the end of 24 weeks follow-up analysis window. Data will be presented overall and by the baseline stratification factors defined in [Table 1](#). Analysis windows at planned end of treat and end of 24 weeks follow-up will be identical to those for the primary endpoint (see [Table 2](#) and [Table 3](#)).
- Categorical changes from baseline in HBsAg (e.g., <0.5, ≥0.5, ≥1, ≥1.5, ≥3 log₁₀ IU/mL) and in HBV DNA (e.g., <1, ≥1, ≥2, ≥3 log₁₀ IU/mL). Change from baseline will be presented at each visit and for the following time periods: up to and including Week 6, up to and including Week 12, up to and including Week 24, up to and including off-treatment Week 24. Data will be presented overall and by the baseline stratification factors defined in [Table 1](#). Data will be summarized using planned visits.
- ALT normalisation (ALT ≤ ULN) over time in absence of rescue medication in participants with baseline ALT > ULN.
- HBe antibody (anti-HBeAg) levels.

Population Summary: Percentage of participants in each category for each treatment arm.

Continuous Variables

Continuous variables for the secondary objective are defined as follows:

- Actual values and change from baseline over time of HBsAg, HBV DNA, and HBeAg levels (only in HBeAg Positive Participants at baseline).
- Actual values and change from baseline over time for HBs antibody (anti- HBsAg) levels.
- Actual values and change from baseline over time for ALT.

Population Summary: Mean values and mean changes from baseline of each variable for participants in each treatment arm.

Time to Event Variables:

A time to event variable for this objective is defined as:

- Time to ALT normalisation in absence of rescue medication in participants with baseline ALT>ULN.

Population Summary: Turnbull's estimator for nonparametric estimation of Time to ALT normalisation in each treatment arm.

ALT normalization is defined in participants with ALT>ULN at baseline as a return to <ULN (ULN = 40 for males and 33 in females). Time to ALT normalization is defined as time from baseline to the first follow-up where subject's ALT has returned to normal.

For participants who withdraw from the study or Participants with ALT>ULN at the end of study (EoS), time to ALT normalization will be censored after the time of the last visit with non-missing ALT value available. Participants who receive rescue medication cannot go on to achieve the event of 'ALT normalization in the absence of rescue medication'; such participants will be censored at the end of the follow up period.

In order to determine if the addition of a PegIFN treatment after completing 12 or 24-weeks of Bepirovirsen delays relapse, an additional time to event variable is defined as follows:

- Time from Bepi EOT to Relapse by HBsAg Categories

Population summary: summary statistics of the time from Bepirovirsen end of treatment to relapse including: N(%) with relapse, mean, standard deviation, median, minimum, and maximum using the number of participants achieving VR at Bepi EOT. Additionally, a Kaplan-Meier plot and associated percentiles will be produced to provide a graphical comparison of time to relapse between treatment arms.

Only participants who were virologic responders at the end of Bepirovirsen treatment will be considered, since they are the only ones who can relapse. Time to relapse is defined as the first time point where the participant can no longer be considered a responder by the primary estimand for the conservative definition. This includes observed elevation(s) in either HBsAg or HBV DNA or rescue medication usage. Generally, time from end of Bepirovirsen treatment to relapse will be calculated from the date of the planned Week 24 or 12 visit (for arms 1 and 2 respectively), where HBsAg<LLOQ and HBV DNA<LLOQ,

until the first visit after the planned Week 24 or 12 visit where HBsAg \geq LLOQ or HBV DNA \geq LLOQ.

4.3.1.2. Durability of Virological Response after Sequential Therapy with 12 Weeks of GSK3228836 Followed by up to 24 Weeks of PegIFN

The estimand strategy supporting this secondary objective is the same strategy defined in Section 4.3.1.1 and focuses on the timepoints following the 24 weeks off-treatment period(i.e., Week 30 and Week 36).

4.3.1.3. Comparison of Efficacy Between Treatment Arms of 12 and 24 Weeks of GSK3228836 Followed by up to 24 Weeks of PegIFN

The estimand strategy for this objective are defined as follows:

- **Population:** Participants with CHB on stable NA therapy, regardless of discontinuation of, interruptions in or adherence to GSK3228836 or PegIFN, had they not been affected by wide disruptive events.
- **Treatment:** 300 mg GSK3228836 for 12 or 24 weeks followed by up to 24 weeks of PegIFN therapy while on stable NA therapy. One treatment comparison between Arms 1 and 2 up to 24 weeks off treatment.

- **Intercurrent Events:**
 - Discontinuation of, interruption in, and non-adherence to GSK3228836 and PegIFN will be analysed as collected (treatment policy).
 - PegIFN ineligibility will be analysed as collected (treatment policy)
 - Participants who have used rescue medication will be incorporated in the definition of the endpoint (composite strategy)
 - For wide disruptive events (such as COVID-19 pandemic) leading to discontinuation of, significant interruption in, or non-adherence to GSK3228836 or PegIFN, data collected after the intercurrent event will be set to missing and the response will be imputed using all available data for participants for whom SVR can be assessed. (hypothetical strategy).

Population Summary: Difference in percentage of participants who achieve SVR for 24 weeks after the planned end of sequential treatment between treatment arms

Categorical Variables

The following categorical variables are defined for this objective:

- Achieving SVR (HBsAg <LLOQ and HBV DNA <LLOQ) at the planned end of sequential treatment and over the 24 weeks follow-up for each treatment arm.

Main Analytical Approach

The secondary efficacy comparison of interest is the difference in sustained virologic response rate for 24 weeks after the planned end of sequential treatment between treatment arms:

- Arm 1 vs. Arm 2 in percentage of participants achieving SVR for 24 weeks after the planned end of sequential treatment, without use of any rescue medication.

Comparison between treatment arms will be made by calculating the difference between the posterior distributions of the response rate in each arm which will be summarised to obtain posterior means and CIs. Samples from the posterior distribution of the response rates in each arm will also be used to obtain posterior probabilities of interest. The point estimates of differences in SVR rate with 95% credible intervals will be calculated for the treatment comparisons described in the estimands. Posterior probabilities $\Pr(\text{Arm 1} - \text{Arm 2} > 0)$ and $\Pr(\text{Arm 2} - \text{Arm 1} > -0.05)$ will be presented to aid selection of treatment regimen.

Model Checking and Diagnostics – MCMC Mixing Diagnosis

The same approach in model checking and diagnostics will be applied as for the primary analysis (Section 4.2.2.3).

